### **EXPECTED OUTCOMES (Aim 1)**

We expect, for our primary outcome, that there will be a positive correlation between post-HD ECV/body weight and the mean IBPS of 0.6. We expect that the standard deviation in our cohort's IBPS will be smaller than that of our preliminary data cohort due to 1) a more homogenous population (see Exclusion criteria 3-8) excluding patients whose blood pressure changes are more likely to be related to ECV-independent comorbidities (autonomic neuropathy, medication non-adherence, advanced heart failure) and 2) calculation of the mean IBPS over 6 treatments, not a single treatment. We expect the ECV/body weight to be higher in men than women, but the correlations between ECV/body weight and IBPS will be similar. We expect that the association between IBPS and *pre*-HD ECV/body weight will not be as strong as with the slopes and *post*-HD ECV/body weight because pre-HD measurements are more reflective of acute, not chronic ECV excess. Based on our preliminary data, we do not expect as strong a correlation will exist with ECV/total body volume and IBPS.

[figure not shown]
### POTENTIAL PROBLEMS AND ALTERNATIVES (Aim 1)

Our hypothesis is strongly supported by our preliminary data. In the unlikely event that our experiment proves this invalid, we will have laboratory data and data on total body volume, dialysis prescription, antihypertensive medication use, and ultrafiltration rates to better understand which factors best associate with IBPS in various subgroups. There are some patients whose intradialytic blood pressure would likely be influenced by ECV-independent factors.

This includes 1) patients with very high amounts of acute and chronic ECV who have extremely high ultrafiltration rates (>13 mL/hr/kg) that may induce intravascular volume depletion in the absence of ECV depletion and 2) patients with large decreases in intradialytic blood pressure related to acute loss of total peripheral resistance (patients with diabetes for many years with autonomic neuropathy, patients with sympathetic nervous system dysfunction, patients taking antihypertensive medications during HD). Our exclusion criteria minimize the risk of these factors impacting our study.

3. AIM 2: The premise for this aim is there is a need for individualized fluid management interventions that minimize mortality risk factors in HD patients. The objective of this aim is to demonstrate how IBPS-based ultrafiltration prescriptions affect ambulatory blood pressure and ECV in hypertensive HD patients. We will test the working hypothesis that after 16-weeks, subjects randomized to our algorithm will have larger reductions in 1) ambulatory blood pressure during the interdialytic period, 2) post-HD ECV/body weight (measured with BIA), and 3) peripheral resistance compared to standard care.

Based on our preliminary data showing a relationship between IBPS and ECV/body weight (**Figure 2**), we have developed an algorithm that

assigns ultrafiltration goals based on the IBSP demonstrated over the prior two weeks. With this algorithm detailed in **Table 2 (below)**, subjects with the most negative slopes will have the least aggressive fluid removal while those with positive slopes will have the most aggressive prescriptions.

**RESEARCH DESIGN (Aim 2):** Our design for Aim 2 will be an un-blinded, randomized clinical trial comparing IBPS based fluid management to standard care.

Patient Population: We will use consecutive sampling to identify eligible participants from our UT Southwestern-affiliated HD units. Inclusion and exclusion criteria are presented in the common approach section. Subjects agreeing to participate will be assigned to one of two study groups based on computer-generated randomization stratified by gender: IBPS-based management or Standard Care.

### Study Procedures:

Baseline Information will be collected after subject enrollment (see Common Approach Elements above).

Standard Care Group: Subjects randomized to standard care will continue to be managed by their individual nephrologists. In our units, 10 different nephrologists manage patients. Each nephrologist evaluates individual patients in person once every 1-2 weeks to ascertain interval subjective events, physical examination, blood pressure, and laboratory data. There are no mandatory changes at any visit. The nephrologist has discretion to change blood pressure medications, target dry weight, and ultrafiltration goals based on his/her individual assessment of the patient's needs.

IBPS-Based Management: Subjects in this arm will have ultrafiltration prescriptions ordered by study personnel based on the IBPS from the prior 2 weeks. We will recalculate IBPS every month to as we expect IBPS to change with gradual ECV reduction throughout the course of the study. At each monthly visit, study personnel will modify the prescription based on the prior 2 weeks of intradialytic blood pressure data.

The specific algorithm used to prescribe the ultrafiltration is shown in **Table 2**. In addition to the ultrafiltration prescribed to achieve the patient's prior dry weight, we will assign an pre-specified percentage of dry weight to

[figure not shown]
TABLE 2: Ultrafiltration Prescription Algorithm for Intervention Group			
Slope	Intervention		
<-9 mmHg/hr	Continue UF prescription. Extend dialysis treatment length		
-9 <x<-4 hr<="" mmhg="" td="">Target Weight Reduction of 0.3% each treatment x1 week	</x<-4>	Target Weight Reduction of 0.3% each treatment x1 week		
-4 <x<+2 hr<="" mmhg="" td="">Target Weight Reduction of 0.4% each treatment x 1 week	</x<+2>	Target Weight Reduction of 0.4% each treatment x 1 week		
>+2 mmHa/hr	Target Weight Reduction of 0.5% each treatment x 1 week		

be removed each treatment for 3 consecutive treatments to establish a new dry weight. After these 3 treatments, we will use this new dry weight as the target weight for ultrafiltration each visit

until the next monthly evaluation. In a given month, the minimal dry weight reduction would be 0% and the maximum would be 1.5% of the target weight. New orders will be placed each month for 4 months.

Our algorithm assigns a graded increase in additional ultrafiltration based on flat or positive IBPS compared to

# **Outcomes** During The Study:

Ambulatory Blood Pressure: The mean ambulatory systolic blood pressure will be the primary dependent variable. We selected this variable because it is the blood pressure metric that best predicts mortality in HD patients[12]. Unlike BIA or NICOM, no subjects that would be excluded from obtaining ambulatory blood pressure measurements in this study. All subjects will have baseline measurements of ambulatory blood pressure at week 0 following a mid-week treatment. It will be repeated at week 16 following a mid-week treatment.

*BIA and NICOM:* At baseline (week 0), all eligible subjects will undergo BIA and NICOM for measurements of ECV/body weight (see Aim 1) and total peripheral resistance index before and after a mid-week treatments. The procedures will all be repeated at week 8 and week 16 following a mid-week treatment.

### **Statistical Analysis Plan and Power Calculation for Sample Size (Aim 2)**

The primary outcome of this aim will be the ambulatory systolic blood pressure from baseline to 16 weeks. Secondary endpoints include ECV/body weight and total peripheral resistance, from baseline to 16 weeks. We will use the two-sample t test to perform the unconditional comparison of the difference in endpoints over time between treatment and control groups. For conditional comparison, we will use the linear mixed effect model to estimate the fixed effect of the treatment group indicator, while adjusting for the fixed effects from baseline variables and time and the random effect within the same patient. We determined our sample size based on known effects of intense ultrafiltration on ambulatory blood pressure reduction. In the DRIP trial[10], systolic blood pressure decreased by 13.9 mmHg in the intense ultrafiltration group and 6.9 mmHg in the standard group (95% CI -12.2 − 1 mmHg) after 8 weeks. We expect a more modest decrease in systolic blood pressure due to our less aggressive approach per treatment. Assuming a standard deviation for the ambulatory systolic blood pressure change of 6 mmHg (this was approximately 2.7 mmHg in DRIP and our study will have a smaller sample size), we will be able to show with 90% power and an alpha of 0.05, that a between group difference ≥2.7 mmHg will occur. If the normality assumption indeed holds in our observed data, this would require 14 subjects per arm, but we will recruit 30 subjects per arm to facilitate simple normality check such as the Q-Q plot. Assuming a 25% dropout rate, we will aim to recruit 74 subjects (37 in each group).

With our sample size (n=74), we will have 85% power to detect a 0.025 difference in the change between groups after 16 weeks in ECV/body weight. This clinically significant difference is consistent with the difference in post-HD ECV/body weight we found in patients with intradialytic hypertension and HD controls [13]. Based on our prior experiences recruiting HD patients for clinical research, we expect that we will be able to enroll 1-2 patients each month (18 patients each year including excluding dropouts).

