# **EXPECTED OUTCOMES (Aim 2)**

We expect the IBPS-based ultrafiltration group to have ≥3 mmHg greater reduction in mean ambulatory systolic blood pressure from baseline to 16 weeks than the standard care group. We expect that such differences could be as high as 7 mmHg based on the DRIP trial. Because our algorithm assigns fluid removal objectively and most hypertensive HD patients have ECV excess that is difficult to identify clinically, we expect that subjects assigned to our algorithm will be assigned more fluid removal over the course of the study than those in the standard care group. We expect the outcomes to include improvement in chronic ECV excess as shown by greater reduction in post-HD ECV and ECV/body weight. We expect to also see reduction in post-HD total peripheral resistance. We do expect ambulatory blood pressure to decrease in the standard care group due to patient motivated lifestyle changes while in a clinical trial. However, we expect that the decrease in blood pressure will be of greater magnitude in our IBPS-based ultrafiltration group as specified above. We expect our algorithm will optimize fluid removal and that the change in post-HD ECV/body weight will be ≥0.025 in the IBPS-based ultrafiltration group compared to standard care.

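### The Aim 2 mixed model estimates a group effect with no group-by-time term; for ambulatory SBP this would be half the week-16 effect if week 0 is a response, and no analysis is named as deciding.

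*Combined protocol and SAP*

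**What the plan says.** **Target.** The Aim 2 working hypothesis is that "after 16-weeks, subjects randomized to our algorithm will have larger reductions in 1) ambulatory blood pressure". Expected Outcomes (Aim 2) anticipates at least 3 mmHg "greater reduction in mean ambulatory systolic blood pressure from baseline to 16 weeks than the standard care group". The estimand is therefore the between-group difference in change from week 0 to week 16.

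**Visits.** Under Outcomes During The Study, ambulatory blood pressure is taken at week 0, and "It will be repeated at week 16 following a mid-week treatment". There is no week-8 value. The week-8 visit belongs to bioimpedance and NICOM, which supply the secondary endpoints ECV/body weight and total peripheral resistance (TPR): "The procedures will all be repeated at week 8 and week 16 following a mid-week treatment".

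**Analyses.** The statistical section for Aim 2 gives an unadjusted analysis: "We will use the two-sample t test to perform the unconditional comparison of the difference in endpoints over time". It then gives an adjusted one, a linear mixed model that will "estimate the fixed effect of the treatment group indicator, while adjusting for the fixed effects from baseline variables and time", plus a random effect for patient. Neither is called primary. The baseline variables are not listed. The section does not say whether week 0 is a response, a covariate or both. The statistical section for Aim 3 later describes the Aim 2 approach to continuous outcomes as a repeated-measures mixed model, which settles none of this.

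**Allocation.** Patients are assigned by "computer-generated randomization stratified by gender" (Research Design, Aim 2).

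**The concern.** The two analyses can answer different questions with the same data. The t test on change estimates the stated target without bias. It makes no regression adjustment for baseline SBP or for the gender stratum, so it gives up some precision.

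The mixed model, as worded, estimates a group main effect. In a model with time but no group-by-time term, that coefficient is an average of the group difference over every visit that enters as a response. If week 0 is one of them, the average includes a visit at which randomisation makes the expected difference zero.

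The adjusted SBP estimate could then be about half the unadjusted one in the same patients, with no rule for which to report as the trial's result.

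**Working it through.** **Inputs.** From the statistical section for Aim 2: SD of change 6 mmHg, 30 per arm, alpha 0.05 (taken as two-sided), difference 2.7 mmHg. From Expected Outcomes (Aim 2): differences of 3 and 7 mmHg. The baseline/week-16 correlation, rho, is not in the document; 0.3 to 0.8 is an assumed range.

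**The plan's own figure.** The plan states 14 per arm for 2.7 mmHg, SD 6 and 90% power. The usual formula gives 2 × 36 × (1.960 + 1.282)² / 2.7² = 103.8, so 104 per arm. The stated figure does not reproduce. That is a separate matter. It matters here only because it explains why power is about 40% at 30 per arm even for the unbiased t test.

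**Step 1: is week 0 a response?** The model adjusts for "baseline variables and time and the random effect within the same patient". If week 16, or the change score, were the only SBP response, each patient would have one record, and neither a time effect nor a patient random effect could be estimated. Both can be estimated only with weeks 0 and 16 as responses.

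**Step 2: what the group coefficient estimates.** Let D be the true week-16 difference. With two visits and no interaction, the coefficient is (0 + D)/2 = D/2. So 2.7 becomes 1.35, 3 becomes 1.5 and 7 becomes 3.5 mmHg. Adding baseline SBP as a covariate does not change this: given baseline, the week-0 response carries no group difference, so the average is still D/2.

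Simulation agrees. Over 200 data sets of 300 per arm with D = 2.7 and rho = 0.7, the mean estimates (absolute values) were:
- group main effect: 1.35
- group main effect with baseline SBP as covariate: 1.36
- group-by-time term: 2.72
- ANCOVA on week 16: 2.72

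**Step 3: power.** Fixing the SD of change at 6 gives a single-visit variance s² = 36 / (2(1 − rho)). Each variance below is multiplied by 2/30 for the group difference, and power comes from the noncentral t distribution.
- t test on change: effect D, variance 36
- Group main effect, no baseline SBP: effect D/2, variance s²(1 + rho)/2
- ANCOVA: effect D, variance s²(1 − rho²) = 36(1 + rho)/2

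Example at rho = 0.5: s² = 36, main-effect variance 27 with effect 1.35, ANCOVA variance 27 with effect 2.7.

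Power at D = 2.7 mmHg:

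| rho | t test on change | main effect | main effect + baseline SBP | ANCOVA |
|---|---|---|---|---|
| 0.3 | 40% | 24% | 45% | 57% |
| 0.5 | 40% | 17% | 43% | 51% |
| 0.7 | 40% | 11% | 41% | 46% |
| 0.8 | 40% | 9% | 40% | 44% |

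The fourth column was simulated as a random-intercept model; its type I error was 2.6% to 4.0%, so it is conservative. At D = 3 and rho 0.5 / 0.7: main effect 20% / 13%, t test 48%, ANCOVA 59% / 54%. At D = 7: main effect 73% / 46%, t test and ANCOVA 99% or more.

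**Step 4: an open choice.** Each test alone holds its level. With equal variances at the two visits, a patient's change and mean are uncorrelated, so under normality the t test and the main-effect test without baseline SBP are independent. If either could be reported as the result, the chance of at least one false positive is 1 − 0.95² = 9.75%. Simulation of 20,000 null trials gave about 9.5% to 9.7% at rho 0.5 and 0.7.

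**Step 5: ECV/body weight and TPR.** Let the week-8 effect be a fraction f of the week-16 effect. With weeks 0, 8 and 16 as responses, the bare group coefficient is (0 + f + 1)/3, which is 33% to 67% of the week-16 effect for f from 0 to 1. With weeks 8 and 16 only it is (f + 1)/2, which is 50% to 100%.

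**The case against.** The strongest reply is that one generic sentence covers three endpoints. Two of them have two post-baseline visits, so time and patient effects make sense there without week 0 as a response. For SBP the same sentence might be meant to collapse to a regression of week 16, or of change, on group and baseline variables, and the coefficient would then be the full effect. The sentence also follows directly on a comparison of change, and it omits an interaction rather than excluding one. This stands in part: the halving is conditional, and another intention is possible. But that reading drops two terms the text names, so the model as written is either diluted or not estimable for the primary endpoint.

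A second reply is that the t test is implicitly primary. It comes first, the sample size uses the SD of change, and the 30 per arm is justified by a normality check. These are fair signals, and if the t test decides, the main result is not diluted. Nothing declares it, however, and the Aim 3 section points to the mixed model for continuous outcomes.

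A third reply is that the low power figures need baseline SBP to be left out. That is correct. With it included, power is 45% to 40%, no worse than the t test, and what remains is a coefficient of half the intended size. Preferring ANCOVA to a valid t test is also a gain in precision and not a correction of bias; at rho 0.7 it moves power from 40% to 46%.

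**Conclusion.** The concern holds. Three facts come straight from the text: ambulatory SBP has only weeks 0 and 16, the mixed model targets a group effect with no stated group-by-time term, and no analysis is named as deciding.

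The halving is exact and does not depend on rho, but it rests on week 0 being a response. That is the only reading under which the stated time and patient effects can be estimated for this endpoint. The power figures rest on the plan's SD of 6, on 30 per arm and on assumed correlations. The loss relative to the t test arises only if baseline SBP is not a covariate.

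Neither test inflates type I error by itself. If the t test decides, the cost is lost precision: ANCOVA variance is (1 + rho)/2 of the change-score variance, so 25% lower at rho 0.5 and 15% lower at 0.7. The further gain from adjusting for gender cannot be sized, because the document gives no gender effect on SBP. The ECV/body weight and TPR ranges depend on an unstated week-8 effect and an unstated choice of response visits. This should be fixed before the analysis.

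**What to change.** In the statistical section for Aim 2:

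- Name one primary analysis: week-16 mean ambulatory SBP regressed on randomised group, baseline ambulatory SBP and gender. An equivalent choice is a longitudinal model with weeks 0 and 16 as responses, baseline means constrained equal across groups, gender as a covariate and a group-by-visit term, with the week-16 contrast as the treatment effect.
- List the baseline variables in advance.
- Keep the t test on change as a supportive analysis.
- For ECV/body weight and TPR, state which visits are responses, include a group-by-visit term and report the week-16 contrast.

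The cost is wording only. Baseline SBP and gender are already collected, and no visit, measurement or patient is added.

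### The Aim 2 primary power claim fails on its own inputs: 2.7 mmHg with SD 6 at 90% power needs about 105 per arm (86 one-sided), not 14, and the planned sample gives about 38% power (51% one-sided)

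*Combined protocol and SAP*

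**What the plan says.** The section Statistical Analysis Plan and Power Calculation for Sample Size (Aim 2) names the test: "We will use the two-sample t test to perform the unconditional comparison of the difference in endpoints over time". It takes an SD of "change of 6 mmHg (this was approximately 2.7 mmHg in DRIP and our study will have a smaller sample size", and claims that "we will be able to show with 90% power and an alpha of 0.05, that a between group difference ≥2.7 mmHg will occur". On the number needed it says "this would require 14 subjects per arm, but we will recruit 30 subjects per arm", the increase being for a normality check. On dropout it says "Assuming a 25% dropout rate, we will aim to recruit 74 subjects (37 in each group". It does not say whether alpha is one-sided or two-sided.

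Expected Outcomes (Aim 2) gives the range of effect in view. At the lower end: "We expect the IBPS-based ultrafiltration group to have ≥3 mmHg greater reduction in mean ambulatory systolic blood pressure". At the upper end: "We expect that such differences could be as high as 7 mmHg based on the DRIP trial".

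**The concern.** The difference of 2.7 mmHg is less than half the assumed SD (2.7/6 = 0.45). Fourteen per arm cannot give 90% power for a standardised difference of that size, so the difference, the SD, the power and the sample size cannot all be right together.

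This calculation sets the size of the whole trial, because the Aim 3 analysis section says its sample size is taken from it. If the claim is wrong, a reader who trusts the 90% would read a null primary result as evidence against a 3 mmHg benefit when the trial had little chance of detecting one.

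Two smaller points sit in the same paragraph. The 25% dropout allowance does not leave the 30 per arm intended. And the reason given for the SD confuses a patient-level SD with a standard error.

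**Working it through.** **Inputs**, all from the Aim 2 power section: two-sample t test on the change, difference δ = 2.7 mmHg, SD σ = 6 mmHg, alpha 0.05, power 90%, 1:1 allocation. Sidedness is not stated, so both are shown.

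**1. Trying to reproduce the 14.** The normal approximation is n per arm = 2σ²(z_α + z_β)²/δ².

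- Two-sided: 2 × 36 × (1.960 + 1.282)²/2.7² = 103.8, so 104. The exact (noncentral t) calculation gives 105.
- One-sided: 2 × 36 × (1.645 + 1.282)²/2.7² = 84.6, so 85. Exact: 86.

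The stated 14 is not reproduced. Other readings:

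| Reading (90% power) | n two-sided | n one-sided |
|---|---|---|
| δ = 2.7, SD 6, as written | 105 | 86 |
| δ = 2.7, SD 6, one-sample formula | about 54 | about 44 |
| δ = 2.7, SD 2.7 | 23 | 18 |
| δ = 7 (13.9 − 6.9), SD 6 | 17 | 14 |

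Only the last row, one-sided, gives 14, and it uses DRIP's difference of 7 mmHg rather than 2.7.

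**2. Completers.** 37 × (1 − 0.25) = 27.75, about 28 per arm. To keep 30 after 25% dropout takes 30/0.75 = 40 per arm. With 37, 30 remain only if dropout is no more than 1 − 30/37 = 18.9%.

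**3. Power for 2.7 mmHg at SD 6** (unadjusted t test, noncentral t):

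| n per arm | Two-sided | One-sided |
|---|---|---|
| 14 (stated as required) | 20.9% | 31.4% |
| 28 (after 25% dropout) | 38.0% | 50.7% |
| 30 (intended) | 40.3% | 53.1% |
| 37 (no dropout) | 48.0% | 60.7% |

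**4. What 28 per arm delivers at SD 6:**

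| Quantity | Two-sided | One-sided |
|---|---|---|
| Power for 3 mmHg | 45% | 58% |
| Power for 5 mmHg | 86% | 92% |
| Power for 7 mmHg | 99% | >99% |
| Difference detectable with 90% power | 5.3 mmHg | 4.75 mmHg |
| Difference detectable with 80% power | 4.6 mmHg | 4.0 mmHg |

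**5. SD needed to rescue the claim.** For 90% power at 2.7 mmHg with 28 per arm, the SD of change could be at most 3.1 mmHg (3.4 one-sided), about half the assumed 6. Conversely, two-sided power for 7 mmHg stays at or above 90% up to an SD of 7.9 mmHg.

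**6. Source of the SD (a query; steps 1 to 5 do not depend on it).** A patient-level SD does not rise because a study is smaller; a standard error does. The DRIP interval quoted in the section implies a standard error of the difference of (12.2 − 1)/3.92 = 2.9 mmHg, or (12.2 + 1)/3.92 = 3.4 mmHg if the upper limit is +1. Both are close to the 2.7 that the plan calls an SD.

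**The case against.** The best defence is that 14 is a sound number with the wrong difference beside it. The section bases the sample size on the known effect of intense ultrafiltration in DRIP, and 7 mmHg at SD 6, one-sided, gives exactly 14. That may be its origin, though this is inference. It does not save the sentence, which attaches 90% power to 2.7 mmHg. The same section also expects a smaller effect than DRIP's, so 7 mmHg is not the plan's base case.

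A second defence is the planned mixed model adjusting for baseline variables, which could reduce residual variance. For 90% two-sided power at 2.7 mmHg with 28 per arm, residual variance would have to fall to (3.06/6)² = 26% of 36, a cut of about 74%. With 14 per arm it would have to fall to about 12%. The plan gives no correlation to support either, and its sample size statement does not invoke adjustment. What stands is that the power figures should be labelled as those of the unadjusted t test.

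Three further points are fair. The gap between 28 and 30 completers is minor: it moves power for 2.7 mmHg from 38% to 40%, the 30 was chosen for a normality check, and 37 looks like 30 × 1.25 = 37.5 rounded down. The printed DRIP interval is unclear in sign, and its midpoint (−6.6 or −5.6) does not equal the 7.0 difference, so the standard error question cannot be settled from these documents. And the 99% for 7 mmHg depends on an SD whose justification is itself in doubt, so it should be stated as conditional.

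**Conclusion.** The concern holds and must be fixed. On the plan's own test, difference, SD, alpha and power, the required number is 105 per arm (86 one-sided), about 7.5 times (6 times) the stated 14. The roughly 28 completers per arm give 38% power (51% one-sided). At SD 6, a true 3 mmHg effect would be missed about 55% of the time two-sided, or 42% one-sided.

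This rests on the SD of 6 mmHg, 25% dropout and an unadjusted comparison of changes. The conclusion does not depend on sidedness or on what DRIP's 2.7 represents. It does not mean the trial is too small for every effect of interest: for 5 to 7 mmHg, two-sided power is 86% to 99% if SD 6 is right.

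**What to change.** Remove the 14 per arm and replace the power sentence with, for example:

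> With 37 randomised per arm and 25% dropout (about 28 evaluable per arm), an SD of change of 6 mmHg and two-sided alpha 0.05, an unadjusted two-sample t test has 90% power for a difference of 5.3 mmHg and 80% power for 4.6 mmHg. Power is about 38% for 2.7 mmHg, 45% for 3 mmHg and, if the SD is 6 mmHg, 99% for 7 mmHg.

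If the test is meant to be one-sided, say so and use the one-sided figures above. If 14 was computed for 7 mmHg, say that instead of pairing it with 2.7.

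State 28 evaluable per arm or, if 30 is required, randomise 40 per arm.

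Drop the smaller sample as the reason for the SD and check whether DRIP's 2.7 is a standard error. If it is, derive the patient-level SD from DRIP's arm sizes, which these documents do not give, and report the detectable difference for that SD as well.

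The restatement rewrites one paragraph, makes the stated power less favourable and needs no extra patients. Keeping 30 evaluable per arm adds 6 patients (80 instead of 74). Keeping 90% two-sided power for 2.7 mmHg would take 105/0.75 = 140 per arm, 280 in total. At the plan's 18 patients a year that is 280/18 = 15.6 years, or 210/18 = 11.7 years if the 18 are completers. Restating the claim is the proportionate course.
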